4.7 Exploratory Endpoints

- Primary and secondary endpoints among subjects with native versus bioprosthetic disease
- Stroke: disabling and non-disabling
- Coronary stenting: snorkel (heterotopic) and orthotopic (through TAVR stent cells), to prevent or treat leaflet-induced coronary obstruction before (preemptive) and after (bailout or cautionary) TAVR.
- Facilitated BASILICA procedure success, as defined in section 0.
- Composite safety (secondary endpoint) assessed at 90 days
- Ability selectively to engage threatened coronary ostia after BASILICA-TAVR
- Acute hemodynamic deterioration in the interval between BASILICA and TAVR
- Outcomes of subjects who participate in live case demonstrations compared with those who do not

Rationale for Exploratory Endpoints

Coronary stenting related to leaflet obstruction is undesirable and may reflect failed or aborted BASILICA, typically in the heterotopic (“snorkel”) position. Orthotopic coronary stenting is

typically required to treat leaflet prolapse related to mechanical avulsion manifest typically as severe acute aortic regurgitation with hemodynamic compromise.

TAVR can render coronary arteries inaccessible for later emergency PCI. We will capture the ability to selectively engage coronary arteries after BASILICA-TAVR.

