10 STATISTICAL CONSIDERATIONS

10.1 Statistical Hypothesis

The objective of this protocol is to test the safety and effectiveness of the TELLTALE guidewire system in accomplishing BASILICA leaflet traversal and laceration to prevent coronary artery obstruction in the study population. The primary efficacy endpoint and the primary safety endpoint are defined in sections 4.4 and 4.5. We will use the data from this study to estimate the event rates for the primary efficacy and safety endpoints. Due to limited sample size, the study is not powered to evaluate any statistical hypotheses based on these endpoints.

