10.4 Statistical Analyses

Exploratory data analysis will assess for missing values and will generate data clarification requests as required. We expect few missing data. If there are missing data to evaluate the primary efficacy endpoint or primary safety endpoint for a study subject, the endpoint with missing information will be considered a failure for the applicable subject. The primary analysis will be based on the intention-to-treat (ITT) population that includes all study subjects. We will also perform an as-treated analysis in a sensitivity analysis.

For the primary efficacy endpoint, primary safety endpoint and secondary endpoint, we will estimate the event rate by the sample proportion of subject who meet the given endpoint with 95% confidence interval. Descriptive statistics will be used to summarize the baseline demographic characteristics, subject and procedure characteristics, and the exploratory endpoints. For continuous variables, the mean (standard deviation) or median (interquartile range) will be presented. For categorical variables, the frequency and the percentage in each category will be presented. Exploratory post-hoc analyses will be performed as unusual observations and novel questions arise, including those requiring additional data abstraction from the source documents or images.

In an exploratory analysis, results including the primary efficacy endpoint for device technical success and 30-day VARC3 safety will be compared with those outcomes from a previously completed study, the NHLBI BASILICA IDE protocol (NCT03381989) of bedside-modified traversal and laceration guidewires. Fisher's exact tests will be used to compare these outcomes between two studies.

The key study results (primary and secondary endpoints) will be analyzed by subgroups including indication (bioprosthetic versus native), site, census region, age (dichotomized by the sample median), non-white status, and sex. For each of the above baseline characteristics, the subgroup differences in the study outcome will be evaluated by the two-sided Fisher's exact test at a significance level of 0.05. For the subgroup analysis of study sites, the sites with smallest number of patients will be combined to have at least 5 subjects in the pseudo-site group.

Statistical analysis will be performed or confirmed by the NHLBI study statistician.

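### Section 10.4 sets a 0.05 criterion for at least 18 subgroup tests, with no multiplicity control or exploratory label: about a 25-45% chance of one or more spurious differences

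*Combined protocol and SAP*

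**What the plan says.** All references are to the combined protocol and SAP.

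- **Main analysis (10.4).** The approach is estimation: "For the primary efficacy endpoint, primary safety endpoint and secondary endpoint, we will estimate the event rate by the sample proportion", with a 95% confidence interval.
- **Subgroups (10.4).** "The key study results (primary and secondary endpoints) will be analyzed by subgroups". The factors are "subgroups including indication (bioprosthetic versus native), site, census region, age (dichotomized by the sample median), non-white status, and sex". Because the list is introduced as an inclusive one, six is a minimum. For each factor the difference is "evaluated by the two-sided Fisher's exact test at a significance level of 0.05".
- **Sites (10.4).** Small sites are pooled: "the sites with smallest number of patients will be combined to have at least 5 subjects in the pseudo-site group".
- **Purpose (10.1).** The data serve to estimate event rates, and "the study is not powered to evaluate any statistical hypotheses based on these endpoints".
- **Exploratory endpoints (4.7).** One of the six contrasts is listed there: "Primary and secondary endpoints among subjects with native versus bioprosthetic disease". Section 10.4 assigns descriptive statistics to exploratory endpoints.

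Neither 10.4 nor any other section adjusts for the number of subgroup tests or calls their p-values nominal. Section 10.4 does use the word exploratory for the comparison with the prior IDE study and for post-hoc analyses, but not for the subgroup tests.

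**The concern.** A stated significance level is a decision rule. A reader of the final report can fairly take any subgroup p-value at or below 0.05 as a difference that the plan undertook to recognise. With 18 or more such tests in 90 subjects, a chance finding by site, region, race or sex is fairly likely, and it would be hard to set aside afterwards because it met the plan's own criterion. Section 5.3 says the study is intended to support commercialization, so such a finding could reach labelling or regulatory discussion.

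The rule can also mislead the other way. At this sample size a non-significant test says little about whether subgroups are alike.

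Finally, the plan treats native versus bioprosthetic in two ways. It is an exploratory endpoint in 4.7, hence descriptive under 10.4, and it is also tested at 0.05 in 10.4.

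**Working it through.** **Number of tests.** Six factors × three endpoints (primary efficacy, primary safety, secondary) = 18, as a minimum. The two Fisher tests against the prior IDE study are labelled exploratory and are not counted.

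**The plan's own figure.** The documents give no familywise error for these tests. The one related probability they state, in the FDA advice quoted in 10.2, reproduces: 1 − (1 − 0.028)^60 = 0.818, which agrees with the stated >80%.

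**Simple reference value.** For 18 independent tests, each with a true size of exactly 0.05: 1 − 0.95^18 = 0.603. This is too high here. Fisher's test falls below its nominal level when events are few, the two safety endpoints overlap, and sites lie within census regions.

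**Size of a single test.** Exact calculation under no difference, two-sided Fisher at 0.05:

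| Common failure rate | 60 v 30 (valve type) | 45 v 45 (age at median) |
|---|---|---|
| 1% | 0.2% | 0.0% |
| 3% | 1.4% | 0.1% |
| 7% | 2.9% | 1.2% |
| 10% | 3.1% | 2.0% |
| 30% | 3.7% | 3.0% |

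**Simulation under no true difference.**

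Inputs from the documents:
- 90 subjects, 30 native and hence 60 bioprosthetic (10.2).
- Up to 15 sites (7.2).
- Prior IDE study, 28 of 30 with successful traversal and laceration, so about 7% failure (3.2).
- Prior IDE study, 21 of 30 free of MACE, so 30% failure (3.2).
- Expected obstruction, 30-day death and stroke of 5%, 3% and 5% (3.2). Their sum, 13%, is used as a rough upper value for inpatient safety failure.
- Interim primary success of 100% in 27 treated subjects, non-adjudicated (3.2).

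Assumptions, because the documents do not give them:
- 14 non-white subjects and 50 men, with other splits also run.
- Either 15 equal sites or 11 unequal pooled sites, in four census regions.
- Every inpatient safety failure also counts as a secondary-endpoint failure.

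Tests with more than two groups used the Fisher (Freeman-Halton) exact test, with p-values from 20,000 simulated tables. Each scenario had 2,500 to 4,000 trials, so the simulation error is about one percentage point: √(0.42 × 0.58 / 4,000) = 0.008.

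| Failure rates: efficacy / safety / secondary | Chance of at least one p ≤ 0.05 |
|---|---|
| 7% / 13% / 30% (prior-study and expected rates) | 0.42-0.44 |
| same, other sex and race splits | 0.40-0.42 |
| 7% / 10% / 30% | 0.42 |
| 5% / 8% / 25% | 0.39-0.41 |
| 2% / 10% / 30% | 0.35-0.37 |
| 2% / 5% / 20% | 0.29-0.34 |
| 0% / 10% / 30% (no technical failures) | 0.32-0.33 |
| 0% / 3% / 30% (no technical failures) | 0.24-0.27 |
| 1% / 3% / 15% | 0.23-0.25 |
| 30% / 30% / 50% (high extreme) | 0.47 |

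At 7% / 13% / 30% the per-test sizes were about 4-6% for site and region (2% for site on efficacy when sites were equal) and about 1-4% for the two-group factors.

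**Power of the same rule.** For the 60 v 30 valve-type test with assumed true failure rates of 5% v 15%, the exact power is 32%. For 10% v 20% it is 22%.

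**The case against.** The strongest reply is that nothing in the plan turns on these tests. The main result is a proportion with a confidence interval. The FDA advice quoted in 10.2 accepts that the study is not hypothesis-based. Valve type is already exploratory in 4.7, and no text says that a subgroup p-value below 0.05 will be claimed as real. This stands as a limit on the consequence. It does not remove the point, because 10.4 sets a criterion for these tests and gives no guidance on how to read them.

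Four stronger readings are tempting, and the documents do not support them:

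- **That 10.1 rules out hypothesis testing, so 10.4 contradicts it.** Section 10.1 says "Due to limited sample size, the study is not powered to evaluate any statistical hypotheses based on these endpoints". That is a statement about power, not a bar on testing. The two sections fit poorly together but do not conflict outright.
- **That the error is 60%, or a firm 40%.** The first needs 18 independent tests of exact size. The second belongs to the upper part of a range that depends on assumptions.
- **That few events make false findings more likely.** The reverse holds: fewer events make Fisher's test more conservative. With no technical failures the six efficacy tests cannot reject at all.
- **That valve type should keep its 0.05 test, or that a Holm correction is needed.** Keeping the test would promote a contrast that 4.7 calls exploratory. Holm would make real heterogeneity still harder to see with 90 subjects.

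**Conclusion.** The point holds in a limited form. Section 10.4 applies an unadjusted 0.05 criterion to at least 18 subgroup tests and gives them no exploratory label. Under no true difference the chance of at least one significant result is about 25-45%, with 0.23 to 0.47 as the extremes of all scenarios run. It is near 40-45% at the prior IDE study's rates and about 25-33% if technical success stays near 100%. The range rests on assumed event rates, site sizes, regions and sex and race splits; the count of tests and the absence of any adjustment do not.

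A reader might infer that the trial's main results are compromised. They are not: the primary and secondary estimates and their intervals do not depend on these tests. What changes is what may be concluded about subgroups. This is a cheap improvement, not a flaw that must be repaired before the results can be used.

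**What to change.** Amend the subgroup paragraph of 10.4 as follows:

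1. Remove the 0.05 criterion from all subgroup comparisons, including native versus bioprosthetic, in line with 4.7.
2. Label the subgroup analyses exploratory. If Fisher p-values are shown, call them nominal and unadjusted for multiplicity.
3. Report the event rate in each subgroup with a 95% confidence interval and, for two-group factors, the difference in rates with its 95% confidence interval.
4. State that a nominal p-value below 0.05 will not be taken as showing a difference, and that a non-significant result will not be taken as showing its absence.

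The cost is wording only, with no change to data, sample size or conduct. The downside is that a real subgroup difference would be described with its interval and not declared significant.

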10.5 Stopping Rule Guidance for Data and Safety Monitoring Board (DSMB)

The mortality observed in the prospective NHLBI BASILICA IDE study (n=30) was 3.3%, and the 12-month mortality was 10% [24]. The 30-day mortality observed in the retrospective multicenter international BASILICA registry (n=214) was 2.8%, and 12-month mortality was 21.5% [4].

In Amendment A, the stopping rules are adjusted to become more conservative, as stipulated by the DSMB before enrollment began. The study will be monitored to ensure that the mortality within 30-days after the procedure does not substantially exceed an anticipated rate. We anticipate the rate of 30-day mortality is 5% or less and determine the stopping rule by a Bayesian approach [36]. The stopping boundary is reached if the posterior probability that the 30-day mortality rate exceeds 5% is at least 90%. We take our prior distribution to be a beta distribution so that our prior clinical opinion is worth 20% of the weight we will place on the new study data, which gives the prior parameters $a = 0.75$, $b = 14.25$. Hence when we make decisions about stopping the study, the data from the study will dominate over the prior opinion.

The following table summarizes the threshold numbers for the stop rule boundary, which would lead to a recommendation to stop the study due to the excess 30-day mortality. The custom calculator is posted at <https://rconnect.nhlbi.nih.gov/CTStopRule/>.

Number of subjects in the stratum	Consider stopping if the number of deaths within 30 days reaches
2 - 5	2
6 - 18	3
19 - 31	4
32 - 46	5
47 - 61	6
62 - 75	7

We investigated the performance of the above stopping rule by a simulation study. In each simulation run, we generated a study with 75 independent Bernoulli trials, each with a true certain 30-day mortality, and compared these outcomes with the above stopping boundary to determine whether the study was stopped. We repeated the simulation 100,000 times and computed the proportion of stopped studies using the above stopping rule. The following table summarizes the performance of this stopping rule:

True 30-day mortality rate	0.025	0.05	0.075	0.1	0.15	0.2
Proportion of Stopped Studies	0.022	0.169	0.454	0.72	0.963	0.997
Average number of subjects	73.8	67.6	56	43.3	24.7	15.6
Average number of 30-day mortality	1.9	3.4	4.2	4.3	3.7	3.1

These simulation results suggest that our stopping rule has a low probability stopping a study when the true 30-day mortality rate is 5% or less, and the probability of stopping a study is high

when the true 30-day mortality rate exceeds 5%. There, we believe that our Bayesian stopping rule for 30-day mortality has satisfactory statistical properties.

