An interim analysis of this open-label study for amendment B (September 2023) was triggered by consent of 15 subjects with native aortic valve failure. At this timepoint 27 subjects were treated by TELLTALE BASILICA TAVR, including 14 with native aortic valve failure. Using non-adjudicated data, the primary success rate is 100%, the incidence of coronary obstruction is 0%, and the incidence of stroke/TIA is 0%. Based on these data we propose amending the protocol in Amendment B to expand the study cohort having native aortic valve failure, from 15 to 30 subjects.

These studies provide reassuring data in support of the BASILICA procedure to prevent coronary artery obstruction in this patient cohort with few good options.

Available literature about risks of coronary obstruction

Reported and expected outcomes of patients undergoing TAVR despite risk of coronary obstruction

Setting	n with CTs evaluated	At-risk population	Cor obstruction in at-risk population	30-day Death	Stroke	Reference
ViV	20 obstructed, 90 control	VTC<4mm	89%	53% (in obstructed population)	0%	VIVID registry [2]
Native AS	28 obstructed, 345 control	coronary height<12mm and SOV width <30mm	87%	41% (in obstructed population)	9%	Multicenter Registry [1]
Native AS	60 obstructed, 60 control	Leaflet height ≥ coronary height AND VTC<4mm	90%	27% (in-hospital death, obstructed)	Not collected	CRT 2020 late breaking trial presentation, not published
VIV and Native	30 attempted BASILICA	Leaflet height ≥ coronary height AND VTC<4mm; Leaflet height ≥ STJ AND VTSTJ<2mm	0%	3%	10%	[3]
VIV and Native	214 attempted BASILICA	Leaflet height ≥ coronary height AND VTC<4mm; Leaflet height ≥ STJ AND VTSTJ<2mm	5%	3%	3%	[4]
VIV and Native	15 attempted BASILICA	Leaflet height ≥ coronary height AND VTC<4mm; Leaflet height ≥ STJ AND VTSTJ<2mm	7%	0%	0%	[26]
VIV and Native	21 attempted BASILICA	Leaflet height ≥ coronary height AND VTC<4mm; Leaflet height ≥ STJ AND VTSTJ<2mm	5%	0%	0%	[27]

Compared with pivotal trials in which all candidates at risk of coronary obstruction are EXCLUDED

Setting	Population	n	Cor obstruction	30-day Death	Stroke	
Native AS	Excluded "Bulky calcified aortic valve leaflets in close proximity to coronary ostia"	348	0%	3.4%	3.8%	PARTNER 1
Native AS	Excluded "Bulky calcified aortic valve leaflets in close proximity to coronary ostia"	1011	0.4%	3.9%	5.5%	PARTNER 2
Native AS	Excluded "Bulky calcified aortic valve leaflets in close proximity to coronary ostia"	496	0.2%	0.4%	0.6%	PARTNER 3

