10.2 Sample Size Determination

The sample size is not statistically derived.

Up to 180 candidates will be consented until 90 subjects undergo attempted TELLTALE BASILICA-TAVR in this protocol.

There is a revised quota of 30 subjects who must have native TELLTALE BASILICA-TAVR of the 90 total enrolled subjects. This is based on initial quota of 15 subjects and subsequent study expansion by 15 additional subjects with native aortic valve failure. All subjects, including the expanded native cohort, will undergo analysis for primary, secondary, and exploratory endpoints.

Rationale for Sample Size

TAVR-induced coronary obstruction is rare but devastating [1, 2]. Therefore the potential patient population is small.

The key clinically meaningful outcome is successful TAVR without coronary obstruction. We believe we are able to accomplish this using bedside-modified guidewires for BASILICA-TAVR.

It is not clear whether BASILICA increases the risk of stroke compared historically against TAVR without BASILICA. Neurological events were identified in our early prospective BASILICA IDE trial (n=30) [3, 24] but not evident in the non-adjudicated BASILICA registry (n=213) [4].

FDA CDRH reviewers transmitted the following recommendation:

We recommend increasing the size of the bioprosthetic valve subgroup to 60 subjects. This is based on a literature review of mortality and stroke rates in ViV TAVR studies that reported an average stroke rate (the lower of the two event rates) of approximately 1.4%. We suggest that the sample size be large enough to have potential to detect whether the stroke rate with TELLTALE BASILICA increases 2-fold or greater compared to clinically reported rates. For an event with anticipated incidence rate of $2 * 1.4\% = 2.8\%$, a sample size of 60 will provide $> 80\%$ probability that at least one stroke event will be observed. While we acknowledge that the study will not be hypothesis-based nor powered to detect differences in stroke/mortality, we believe these are important endpoints to consider when assessing safety and effectiveness of the BASILICA procedure with TELLTALE device, and will be incorporated into our final assessment of the totality of data. The suggested sample size of 60 provides reasonable confidence that the sample size is large enough to detect a rare event.

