The bioprosthetic and native valve subgroups do not necessarily need to be balanced in size. We continue to believe that if they are not balanced, that enrollment should be weighted in favor of the bioprosthetic group, since this group appears more likely to have adverse events. As noted above, we suggest that the bioprosthetic group sample size be increased to 60. You may consider maintaining an n=15 native valve sample size, for a total sample size of n=75.

The investigators accept this recommended sample size.

In amendment B, the sample size is increased from 15 to 30 among subjects with native aortic valve failure, for a total sample size of 90.

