15 VERSIONS

Version	Revision
2022-11-30	First FDA approved version
2023-05-25	
• Increase number of sites from 10 to 15• More-conservative stopping rules, as stipulated by DSMB• More-focused reporting of abnormal blood tests as adverse events• Clarification that only one post-TAVR troponin measurement is required, to resolve inconsistency between section 2.4 text and Schedule of Activities• Reference to upcoming IFU revisions for possible alternative guiding catheters• Telephone/electronic consent allowed, for screening only• Housekeeping, list additional exploratory endpoints• Additional recipient of anonymized research data• Additional/optional imaging exams (coronary arteriography and CT) if obtained in the course of standard medical care are transmitted to NHLBI for analysis.• Lengthened allowable window for baseline CT scan

	
• Updated background on global reported clinical experience• Clarify CEAC endpoint review covers only 30d data, when primary and secondary endpoints assessments are due
2023-10-01	
• Study expansion to 15 additional subjects with native aortic valve failure, after initial enrollment quota of 15 is met, in coordination with CDRH.• Clarify ongoing proctorship may be offered in-person or via telepresence, and other housekeeping changes.
2024-10-31	
• Increase number of candidates allowed to be screened, to 180 (should have been requested with Amendment B)

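### The mortality stopping rule in Section 10.5 still describes a 75-subject trial, although the current sample size is 90

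*Combined protocol and SAP*

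**What the plan says.** Section 10.2 gives the history of the sample size. The regulator suggested 60 bioprosthetic and 15 native subjects, "for a total sample size of n=75", and the investigators accepted. Amendment B then doubled the native group, "for a total sample size of 90". The same section says that screening continues "until 90 subjects undergo attempted TELLTALE BASILICA-TAVR in this protocol", and Sections 2.1 and 5.1 also give 90.

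Section 10.5 dates its rule to the earlier amendment: "In Amendment A, the stopping rules are adjusted to become more conservative". The boundary is reached when the posterior probability that 30-day mortality exceeds 5% is at least 90%. The prior is Beta(0.75, 14.25), chosen so that "our prior clinical opinion is worth 20% of the weight we will place on the new study data". The last row of the boundary table covers 62 to 75 subjects, with a threshold of 7 deaths. For the performance table, "we generated a study with 75 independent Bernoulli trials". Section 10.5 concludes that the rule's properties are satisfactory. Section 11.7 describes the rule as non-binding guidance.

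**The concern.** Three items in Section 10.5 are tied to a total of 75: the end of the boundary table, the 20% prior weight and the performance table. Nothing elsewhere in the protocol supplies a boundary or a performance figure for 90. The Section 15 version log shows that another number overlooked at Amendment B, the screening cap, was later corrected with the remark that it "should have been requested with Amendment B". That is background only. The finding rests on the mismatch within the current text.

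Two things are at stake. The first is the threshold for the last 15 subjects, where a reader must improvise. The second is the stated chance of stopping a trial with acceptable mortality, which belongs to a smaller study. The gap is likely to be reached: by the protocol's own figure, a trial with a true mortality of 5% gets past subject 75 with probability 1 − 0.169 = 0.831, given a check after every subject.

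**Working it through.** **Inputs.** From Section 10.5: prior Beta(0.75, 14.25), reference rate 5%, posterior criterion 0.90, and the printed boundary and performance tables. From Section 10.2: totals of 75 (before Amendment B) and 90 (current).

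**Boundary.** For each n, the threshold is the smallest d for which P(rate > 0.05) ≥ 0.90 under Beta(0.75 + d, 14.25 + n − d).

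- Up to n = 75 this gives 2–5: 2; 6–18: 3; 19–31: 4; 32–46: 5; 47–61: 6; 62–75: 7. Every printed row is reproduced.
- Beyond 75, the posterior probability with 7 deaths is 0.907 at n = 75, 0.902 at n = 76, 0.897 at n = 77 and 0.826 at n = 90. With 8 deaths it is 0.953 at n = 77 and 0.908 at n = 90. The same rule therefore continues as 62–76: 7 and 77–90: 8.

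**Prior weight.** a + b = 0.75 + 14.25 = 15. Then 15/75 = 20.0% and 15/90 = 16.7%. The 20% sentence does not itself print 75, so the link is inferred. The table header refers to a stratum, but the strata implied by the current design (60 and 30) would give 25% and 50%, so only 75 fits.

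**Performance.** I used an exact recursion over independent Bernoulli outcomes, with a check after every subject and each outcome known at once.

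| True 30-day mortality | 2.5% | 5% | 7.5% | 10% | 15% | 20% |
|---|---|---|---|---|---|---|
| Stopped, printed (75) | 0.022 | 0.169 | 0.454 | 0.72 | 0.963 | 0.997 |
| Stopped, recomputed (75) | 0.022 | 0.169 | 0.452 | 0.723 | 0.963 | 0.998 |
| Average subjects, printed (75) | 73.8 | 67.6 | 56 | 43.3 | 24.7 | 15.6 |
| Average subjects, recomputed (75) | 73.8 | 67.6 | 56.1 | 43.2 | 24.6 | 15.6 |
| **Stopped (90)** | 0.022 | 0.184 | 0.500 | 0.779 | 0.981 | 0.999 |
| **Average subjects (90)** | 88.5 | 80.0 | 64.0 | 47.1 | 25.0 | 15.6 |
| **Average deaths (90)** | 2.2 | 4.0 | 4.8 | 4.7 | 3.8 | 3.1 |

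The printed values agree with a 75-subject trial within rounding and simulation error.

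**Ways a reader might fill the gap.**

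- *Carry 7 forward to 90.* This departs from the 90% criterion from subject 77. Stopping becomes 0.224 at a true 5% (against 0.184), 0.574 at 7.5% (against 0.500) and 0.836 at 10% (against 0.779).
- *Apply no boundary after 75.* Stopping stays at the 75-subject values, a loss of 0.015 at 5%, 0.0475 at 7.5% and 0.056 at 10%. Average subjects rise by at most about 0.3.
- *Rescale the prior to keep 20% of 90.* The prior becomes Beta(0.9, 17.1). The threshold rises by one death at n = 5, 18, 46, 61 and 76 and is unchanged elsewhere. Stopping is 0.019/0.175/0.489/0.772/0.980/0.999.

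**The case against.** The best case against is that this is a stale table and little more. The prior and criterion are stated in general form and a calculator is cited, so the threshold at any n is already determined. Every printed row remains valid, and the rule is meant to assist the DSMB rather than bind it. Even with no boundary after 75, average subjects barely move. Carrying 7 forward errs towards earlier stopping, which is the cautious direction for a mortality rule. A lower prior weight only strengthens the stated intention that the data dominate. All of this stands, and it is why the effect is called modest. It does not make the printed performance figures or the 20% statement correct for the current trial.

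Two further points stand as qualifications. First, all the probabilities assume a check after every subject, whereas Section 11.7 has the DSMB review progress every six months, or more often on request. If checks took place only at 45 and 90 subjects (an assumption for illustration), stopping at a true 5% would be about 0.12, a larger shift than that from 75 to 90. Second, whether to keep or rescale the prior is for the sponsor and DSMB to decide. Stopping probabilities differ by only about one percentage point at most, but rescaling would loosen early thresholds in a rule that the DSMB had asked to be made more conservative.

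**Conclusion.** The concern holds. Section 10.5 is correct for 75 subjects and has not been carried over to the 90 now planned. The missing thresholds are 7 at subject 76 and 8 for subjects 77–90. The chance of stopping is understated by 1.5 points at a true 5% (0.184 against 0.169), 4.6 points at 7.5% (0.500 against the printed 0.454) and 5.9 points at 10% (0.779 against the printed 0.72). The prior weight is 16.7%, not 20%. These figures rest on the protocol's own prior and criterion, independent outcomes, and a check after every subject with 30-day status known at once. The consequence is limited, but the correction is certain, concerns mortality monitoring and costs little, so it should be made.

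**What to change.** Keep Beta(0.75, 14.25) and the 90% criterion, and obtain sponsor and DSMB acknowledgement.

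1. Change the last boundary row to 62–76: 7, and add 77–90: 8.
2. Rerun the simulation with 90 subjects and replace the performance table. The exact values to expect are in the 90-subject rows above. State beside the table that it assumes a check after every subject with outcomes known at once.
3. Restate the prior weight as about 17% of the data (15/90), and do not rescale the prior.

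The interim look for Amendment B reported that "At this timepoint 27 subjects were treated by TELLTALE BASILICA TAVR", and more data will have accrued since. The added rows nonetheless follow from a prior and criterion fixed before enrollment, and no threshold at or below 75 moves.

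Secondary wording changes for the same edit:

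- Say study rather than stratum in the table header.
- Replace the description of stopping as highly probable above 5% with the figures (about 50% at 7.5% and 78% at 10%).
- State when the boundary is checked, and whether n counts subjects treated or subjects with a known 30-day outcome. The simulated rule corresponds to the latter. The choice can matter: 3 deaths among 18 known outcomes meet the boundary (threshold 3), but with 8 more subjects pending, n = 26 treated has a threshold of 4.

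The cost is one amendment to Section 10.5, one rerun of the existing calculator and simulation, and a disclosed chance of stopping at a true 5% that rises from 16.9% to 18.4%. Endpoints, visits and sample size do not change.

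### Section 10.5 calls the chance of stopping high once 30-day mortality exceeds 5%, but its own table gives 45% at 7.5%

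*Combined protocol and SAP*

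**What the plan says.** Section 10.5 sets a Bayesian monitoring rule for 30-day mortality. The reference rate is given thus: "We anticipate the rate of 30-day mortality is 5% or less and determine the stopping rule by a Bayesian approach". The criterion is: "The stopping boundary is reached if the posterior probability that the 30-day mortality rate exceeds 5% is at least 90" per cent. The prior is Beta(0.75, 14.25), described as carrying 20% of the weight given to the study data. A boundary table, headed "Consider stopping if the number of deaths within 30 days reaches", runs from 2 to 75 subjects.

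For the rule's performance, "we generated a study with 75 independent Bernoulli trials, each with a true certain 30-day mortality". The plan continues: "We repeated the simulation 100,000 times and computed the proportion of stopped studies using the above stopping rule". The printed proportions stopped are 0.022, 0.169, 0.454, 0.72, 0.963 and 0.997 at true rates of 2.5%, 5%, 7.5%, 10%, 15% and 20%.

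The closing paragraph sums up these results thus: "low probability stopping a study when the true 30-day mortality rate is 5% or less, and the probability of stopping a study is high" for rates above 5%. It also calls the rule's statistical properties satisfactory. Neither adjective is given a number. Section 11.7 describes the rule as non-binding guidance.

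**The concern.** The closing sentence puts the change from a low to a high chance of stopping at 5%. The table directly above it does not. At 7.5%, which is 1.5 times the reference rate and 2.5 times the 3% expected in section 3.2, fewer than half of simulated studies stop. No rate between 5% and 7.5% is tabulated, so the table does not show how slowly the probability rises just above the limit.

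This sentence is the plan's only stated justification for its only quantitative stopping rule. The DSMB has to decide how much weight to give to a boundary that has not been reached, and an overstated summary makes that harder.

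**Working it through.** **Inputs, all from section 10.5.** Reference rate 5%; posterior threshold 0.90; prior Beta(0.75, 14.25); boundary of 2 deaths at n = 2–5, 3 at 6–18, 4 at 19–31, 5 at 32–46, 6 at 47–61 and 7 at 62–75; 75 independent outcomes, with the boundary checked after each subject.

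**Step 1: prior.** The mean is 0.75 / (0.75 + 14.25) = 0.05. The weight is 0.75 + 14.25 = 15, and 15 / 75 = 20%, as described.

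**Step 2: boundary.** For each n, find the smallest number of deaths s with 1 − F(0.05; 0.75 + s, 14.25 + n − s) ≥ 0.90, where F is the beta distribution function. Every printed row from n = 2 to n = 75 is reproduced.

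**Step 3: chance of stopping at N = 75.** Exact forward recursion over the number of deaths, absorbing any path that reaches the boundary:

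| True rate | Plan (simulated) | Exact |
|---|---|---|
| 2.5% | 0.022 | 0.0218 |
| 5% | 0.169 | 0.1691 |
| 6% | not given | 0.2732 |
| 7.5% | 0.454 | 0.4522 |
| 8% | not given | 0.5122 |
| 10% | 0.72 | 0.7226 |
| 11% | not given | 0.8023 |
| 15% | 0.963 | 0.9631 |
| 20% | 0.997 | 0.9975 |

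The plan's figures reproduce to within 0.003. The chance of stopping reaches 50% at a true rate of about 7.9%, 80% at about 11.0% and 90% at about 12.8%.

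**Step 4: what a boundary not reached can look like.** Six deaths in 75 stays below the last limit of 7, and is possible if the sixth death comes after subject 61. The observed rate is 6 / 75 = 8.0%, with an exact 95% CI of 3.0% to 16.6%. The posterior is Beta(6.75, 83.25), which puts a probability of 0.815 on a rate above 5%. That is below 0.90, so the rule does not trigger, but it is far from evidence of 5% or less.

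**Step 5: current size.** Section 10.2 now gives 90 subjects, so the rule has to be extended. Two choices of prior are possible:

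- Keep Beta(0.75, 14.25). The criterion gives 7 deaths at n = 76 and 8 at n = 77–90.
- Keep the 20% weight instead: 0.20 × 90 = 18, 0.05 × 18 = 0.9 and 18 − 0.9 = 17.1, so Beta(0.9, 17.1). The boundary moves slightly (3 deaths from n = 5, 8 from n = 76).

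| True rate | N = 90, Beta(0.75, 14.25) | N = 90, Beta(0.9, 17.1) |
|---|---|---|
| 5% | 0.184 | 0.175 |
| 7.5% | 0.500 | 0.489 |
| 10% | 0.779 | 0.772 |

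The picture is the same under either prior.

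**The case against.** The strongest reply is that nothing is hidden. The 0.169 and 0.454 are printed just above the sentence, the DSMB itself stipulated the more conservative rule, and section 10.5 states the aim as keeping mortality from substantially exceeding the anticipated rate. Against that aim, 72% at 10% and 96% at 15% are reasonable. This stands as a defence of the rule. It does not rescue the sentence, which drops the qualifier and claims a high chance for any rate above 5%. Neither 27% at 6% nor 45% at 7.5% is high in any ordinary sense.

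The objection to criticising the other half of the sentence largely stands. The range at or below 5% includes 2.2% at 2.5%, 3.8% at 3% and 8.9% at 4%. The documents set no benchmark that 16.9% at 5% fails.

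A reader might go further and infer three things that the documents do not support:

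- **That the boundary or simulation is wrong.** Both reproduce.
- **That the DSMB is assured of dependable detection above 5%, or that a completed study would be taken as proof of 5% or less.** No section says either. Section 10.1 says the study estimates rates and is not powered for hypotheses, and section 11.7 says the rule assists decisions and does not automate them.
- **That a rate of 7.5% would go unseen about half the time.** Sites report deaths within 24 hours or 3 working days (section 14.2), the adjudication committee reviews deaths within 30 days (section 11.6), and the DSMB reviews progress every six months (section 11.7). Not reaching the boundary is different from nobody noticing.

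**Conclusion.** The point holds as a misstatement in the summary sentence, not as an error in the rule. The chance of stopping is 27% at 6%, 45% at 7.5% and 72% at 10%. It becomes likely only at about twice the reference rate, and reaches 80% near 11%. The 17% at exactly 5% is about one stop in six and should be shown as a number; whether it is acceptable is for the sponsor and the DSMB to judge.

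The N = 75 figures rest only on the plan's own boundary and independent outcomes checked subject by subject. The N = 90 figures also assume that the same 90% criterion is extended and applied to all 90 subjects together, although the table's first column refers to subjects in a stratum. They depend on the choice of prior by about one percentage point or less at the three rates shown, which does not alter the conclusion.

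**What to change.** In section 10.5, replace the concluding sentence with the stopping probabilities themselves. For 75 subjects these are about 2% at 2.5%, 17% at 5%, 45% at 7.5%, 72% at 10% and 96% at 15%. State that stopping is likely only for rates well above 5%, about 10% or more, and that not reaching the boundary does not by itself establish mortality of 5% or less.

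Then re-run the calculation for 90 subjects, say which prior is used and to which group of subjects the table applies, and print those figures instead.

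A separate 95% CI for 30-day mortality would be a useful optional addition. Section 10.4 promises an interval for the 30-day safety composite, which contains death, but not for death alone.

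The cost is a few lines of text and one short calculation. The 90% criterion and the 5% reference rate need not change. The downside is that the rule's stated properties will look less favourable.
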